#### Follow-up for ineligible patients who discontinue protocol treatment

For patients who are deemed ineligible after registering to the trial, who start treatment, but then discontinue study treatment, the same data submission requirements are to be followed as for those patients who are eligible and who discontinue study treatment.

#### Follow-up for patients who are registered, but who never start study treatment

For all study participants who are registered to the trial but who never receive study intervention (regardless of eligibility), the follow-up requirements are specified below:

Baseline and off-treatment notice data submission required. See the Data Submission Schedule accompanying the All Forms Packet.

#### **13.0 STATISTICAL CONSIDERATIONS**

#### 13.1 Overview

This randomized four-arm, double-blind, placebo-controlled phase II trial will assess the efficacy and safety of oxybutynin for reducing hot flash scores in men receiving androgen deprivation therapy. The primary endpoint of this phase II trial is hot flash scores at 6 weeks post-randomization. All analyses will follow an intent-to-treat approach that includes all randomized patients who meet eligibility criteria.

#### 13.2 Study Design

Patients will be randomly assigned to oxybutynin at 2.5 mL twice daily, oxybutynin at 5.0 mL twice daily, placebo at 2.5 mL twice daily, or placebo at 5.0 ml twice daily in a 2:2:1:1 ratio according to the dynamic allocation scheme. Stratification factors will include daily hot flash frequency at baseline (4 to 9 hot flashes per day versus 10 or more hot flashes per day), hot flash duration at baseline (less than 9 months versus 9 or more months), and number of prior hot flash therapies (0 versus 1 or more). The study design includes two placebo arms to match the dose of the two oxybutynin arms; however, patients randomized to the two placebo arms will be combined to form a single placebo arm for analysis. All analyses will follow an intent-to-treat approach that includes all randomized patients who meet eligibility criteria.

#### **13.3** Study Endpoints

Important endpoints for this phase II trial relate to (1) efficacy of oxybutynin as measured by hot flash scores (primary) and hot flash frequency, (2) safety as measured by the presence of CTCAE v5.0-determined grade 3 or higher adverse events, (3) tolerability as measured by relevant patient-reported symptoms on the Symptom Experience Questionnaire (Appendix V), (4) feasibility regarding the conduct of this trial as measured by patient accrual and treatment adherence, and (5) patient-reported quality of life and hot flash interference as measured by the Hot Flash Related Daily Interference Scale (HFRDIS; Appendix VI). Treatment adherence rates will be calculated by dividing the number of patients who completed treatment per protocol by the number of patients who started treatment. Hot flash scores and frequencies will be measured by patients' hot flash diaries (Appendix IV). Daily hot flash scores will be computed by multiplying the frequency of each hot flash grade within a 24-hour period by the severity of the hot flash (grade 0: none, 1: mild, 2: moderate, 3: severe, and 4: very severe) and then summing all the values. Weekly hot flash scores will be computed by averaging these hot flash scores across the 7 days of each week. Weekly hot flash scores will be computed as long as hot flash scores from at least 1 of the 7 days of each week are available. However, the number of missing (daily) hot flash scores each week will be tabulated.

#### 13.4 Analysis Plan

**To assess efficacy**, a mixed model will be estimated that includes baseline and weekly hot flash scores across the 6-week treatment period. The mixed model will include a fixed intercept; fixed effect for time, arm, and arm by time interaction; and residual covariance matrix based on the observed covariances. Alternative structures will be investigated for the residual covariance matrix, with final selection based on convergence of the mixed model and minimization of the Akaike information criterion. Stratification factors used in the randomization as well as baseline patient characteristics and prognostic factors may be included in the mixed model as covariates if imbalances across arms occur. For this mixed model, time will be treated as nominal (not continuous), such that the mixed model will not be making assumptions about the trajectory of

patients' hot flash scores over time. Estimates from the mixed model will be used to construct 90% confidence intervals for mean differences in hot flash score reduction from baseline to 6 weeks post-randomization between the oxybutynin and placebo arms (i.e., Arm A versus Arms C and D combined; Arm B versus Arms C and D combined). To control the Type I error rate, a fixed sequence procedure will be employed such that the following two tests will be sequenced rather than conducted simultaneously. Hot flash score reduction from baseline to 6 weeks will be compared across patients assigned to oxybutynin at 5.0 mL twice daily (Arm B) and patients assigned to placebo (Arms C and D combined) using a contrast estimated via the mixed model. The contrast will involve a two-sided t-test with a nominal significance level of  $\alpha = .10$ . If and only if this test is significant, hot flash score reduction from baseline to 6 weeks will be formally compared across patients assigned to oxybutynin at 2.5 mL twice daily (Arm A) and patients assigned to placebo (Arms C and D combined) using a second contrast estimated via the mixed model. This contrast will also involve a two-sided *t*-test with a nominal significance level of  $\alpha = .10$ . The proposed sequencing is based on the assumption that the effect of oxybutynin will increase monotonically with respect to dose. If p < .10 for both tests, we will conclude that both dosing schedules significantly improved hot flash scores at 6 weeks relative to placebo. If  $p \le .10$  for the first test but p > .10 for the second test, we will conclude that the higher dosing schedule significantly improved hot flash scores at 6 weeks relative to placebo but that the lower dosing schedule did not significantly improve hot flash scores at 6 weeks relative to placebo. Finally, if p > .10 for the first test, we will conclude that neither dosing schedule significantly improved hot flash scores at 6 weeks relative to placebo. In practice, if p > .10 for the first test, we will still conduct the second test, but as an exploratory analysis rather than as a primary analysis. We will also conduct a responder analysis at 6 weeks comparing the proportion of patients who experience a clinically significant improvement in hot flash scores since baseline across the oxybutynin and placebo arms using Fisher's exact test,  $\chi^2$  test, or logistic regression. Stratification factors used in the randomization as well as baseline patient characteristics and prognostic factors may be included in the logistic regression model as covariates if imbalances across arms occur. A clinically significant improvement will be defined as a 50% or greater reduction in hot flash scores since baseline based on preliminary evidence suggesting that patients consider a 50% or greater reduction in frequency of moderate to severe hot flashes to be a meaningful improvement.[41, 42] Patients who experience a 50% or greater reduction in hot flash scores since baseline will be deemed responders, while the remaining patients (including those with missing hot flash scores) will be deemed non-responders. As an exploratory analysis, we will investigate whether these efficacy results differ when using a single day rather than a full week to define patients' baseline hot flash scores.

Weekly hot flash frequencies (as opposed to weekly hot flash scores) will be compared across the oxybutynin and placebo arms in a manner similar to above using a mixed model that accounts for the observed distribution of weekly hot flash frequencies. A fixed sequence procedure will be employed. For the responder analysis, patients who experience a 50% or greater reduction in hot flash frequency since baseline will be deemed responders, while the remaining patients (including those with missing hot flash frequencies) will be deemed non-responders. Finally, consistency of the results will be assessed across the various methods used to evaluate the efficacy of oxybutynin in this trial (i.e., hot flash scores versus hot flash frequencies, mean differences versus 50% or greater reduction since baseline, single day versus full week to define patients' baseline hot flash scores).

**To assess safety**, the proportion of patients experiencing a grade 3 or higher adverse event will be summarized by arm. We expect this proportion to be extremely low for all arms.

To assess tolerability, mixed models similar to the one described above will be estimated that include baseline and weekly patient-reported symptoms as measured by the Symptom

Experience Questionnaire (Appendix V) across the 6-week treatment period. A single mixed model will be developed for each patient-reported symptom. Estimates from the mixed models will be used to construct 90% confidence intervals for mean differences in patient-reported symptoms between the oxybutynin and placebo arms (i.e., Arm A versus Arms C and D combined; Arm B versus Arms C and D combined) at 6 weeks post-randomization. Contrasts estimated via the mixed models will involve a two-sided *t*-test with a nominal significance level of  $\alpha = .10$ .

**To assess feasibility**, the time required to accrue 87 patients will be reported. To move forward with a phase III trial, an average accrual rate of 4 patients per month (starting 4 months after enrollment begins, to account for the time required for multiple institutions to activate the trial) would be desired. The treatment adherence rate (i.e., the number of patients who completed treatment per protocol divided by the number of patients who started treatment) will be summarized by arm.

To assess patient-reported quality of life and hot flash interference, mixed models similar to the one described above will be estimated that include patients' scores on the HFRDIS (Appendix VI) across the 6-week treatment period. A single mixed model will be developed for each HFRDIS item. Estimates from the mixed models will be used to construct 90% confidence intervals for mean differences in patient-reported quality of life and hot flash interference between the oxybutynin and placebo arms (i.e., Arm A versus Arms C and D combined; Arm B versus Arms C and D combined) at 6 weeks post-randomization. Contrasts estimated via the mixed models will involve a two-sided *t*-test with a nominal significance level of  $\alpha = .10$ .

Attempts to minimize **missing data** will be made through site training and data monitoring (e.g., form delinquency notifications, queries; see Section 6.1.3). The proportion of, and reported reasons for, missing data will be presented by time point and arm. Correlation analysis and logistic regression analysis will be used to examine whether baseline patient characteristics and prognostic factors predict missingness. The primary analysis will provide unbiased parameter estimates under a missing completely at random or missing at random mechanism. However, a sensitivity analysis will be conducted to assess the robustness of the results across various assumptions about the missing data.

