#### **1.2** Oxybutynin for Hot Flashes

Oxybutynin is an anti-cholinergic agent which is available in both oral and transdermal formulations. Currently, oxybutynin is approved by the Food and Drug Administration (FDA) for use in managing overactive bladder symptoms. Additionally there are randomized trial data supporting off label use for the management of hyperhidrosis, with studies showing that this effect is equal across both genders.[22-24] Oxybutynin has a very good safety profile, with the most common reported adverse effects being xerostomia, drowsiness, dizziness, mild cognitive effects, and urinary retention, which are typically mild in severity and resolve with discontinuation, if not tolerable.[25]

In 2007, a manuscript reported retrospective data that supported the efficacy of oxybutynin for managing refractory hot flash symptoms in 52 cancer patients, including four men with ADT-

induced hot flashes.[26] The promising results of this study, which suggested a 70% response rate to oxybutynin with acceptable toxicity, led to the development of Phase III, double-blind, randomized trials comparing oxybutynin to placebo in women with hot flashes.[27, 28] One such trial demonstrated that moderate doses of oxybutynin substantially decreased hot flashes with mild to moderate toxicity. [27] More recently, our group completed another study which compared oxybutynin at doses of 2.5 and 5.0 mg BID to placebo in women with symptomatic hot flashes. These results were presented as an oral abstract at the 2018 San Antonio Breast Cancer Symposium, and showed that hot flash scores were significantly reduced from baseline in both the 2.5 mg (-10.6, SD 7.7) and 5.0 mg (-16.9, SD 15.6) treatment arms compared to placebo (-5.7, SD 10.2). Additionally, hot flash frequency was significantly improved for patients receiving both dose levels of oxybutynin (2.5 mg=60% reduction, 5.0 mg=77% reduction) over those treated with placebo (27% reduction). Reported treatment-related adverse effects for participants were typically mild and there was no difference in the discontinuation of the study drug between the oxybutynin and placebo arms. [28]

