#### 11.1 Baseline Symptom Determination (Appendix II)

The baseline symptoms determination is completed after registration and randomization but prior to initiation of study treatment. This form has patients record the number of total hot flashes they experience on a daily basis, along with the number of hot flashes according to severity (mild, moderate, severe, or very severe) over the first 7 days of the study period. It is estimated that completing the baseline symptom determination will take 3-5 minutes daily. Questionnaires should be returned to the investigator at the end of the baseline week (week 1) and at the end of treatment (i.e., after the 7th week following study entry). The patient should be supplied with two addressed/stamped envelopes for returning the forms.

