#### 13.5 Sample Size and Power

As this is a pilot trial, the sample size was determined based on feasibility and logistical considerations rather than on power for hypothesis testing. We aim to enroll 26 evaluable patients per oxybutynin arm and 13 evaluable patients per placebo arm (i.e., 78 evaluable patients total). For the primary aim, 26 evaluable patients per oxybutynin arm and 13 evaluable patients per placebo arm with 6 weekly hot flash scores provide 76% power to detect a mean difference in hot flash score reduction from baseline when comparing each oxybutynin arm (5.0 mL twice daily or 2.5 mL twice daily to the placebo arm (both placebo arms combined) based on a two-sided *t*-test estimated via a mixed model, nominal significance level of  $\alpha = .10$ , intraclass correlation of .50, and population standardized mean difference of 0.50 (i.e., Cohen's convention for a moderate effect size)[44]. In a similar study in women, Cohen's *d* equaled 0.85 when comparing the higher dose oxybutynin arm (2.5 mL twice daily escalated to 5.0 mL twice daily) to the placebo arm [45]. An additional 9 patients will be accrued to account for a 10% loss in sample size due to ineligibility, major treatment violation, or cancellation. Maximum projected accrual is, therefore, 87 patients.

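### The primary mixed model lets baseline means differ by arm; a common baseline mean would tighten the week-6 comparison with no new data

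*Combined protocol and SAP*

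**What the plan says.** Section 13.4 (Analysis Plan) says that "a mixed model will be estimated that includes baseline and weekly hot flash scores across the 6-week treatment period", with time as a nominal factor. The mean structure is given as "The mixed model will include a fixed intercept; fixed effect for time, arm, and arm by time interaction". The primary intervals and tests concern "mean differences in hot flash score reduction from baseline to 6 weeks post-randomization between the oxybutynin and placebo arms", with the 5.0 mL arm tested first and the 2.5 mL arm second, each at two-sided α = .10.

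Covariates are optional. Stratification factors, baseline characteristics and prognostic factors "may be included in the mixed model as covariates if imbalances across arms occur". Nothing in the section sets the baseline means equal across arms or adjusts the primary model for the baseline score.

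On timing, Section 11.1 says: "The baseline symptoms determination is completed after registration and randomization but prior to initiation of study treatment". Sections 7.0 and 7.1 confirm that no study medication is taken in the first seven days. Section 13.2 lists among the stratification factors "daily hot flash frequency at baseline (4 to 9 hot flashes per day versus 10 or more hot flashes per day"). Section 4.5.2 has these factors recorded before assignment, so they precede the diary week that defines baseline.

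**The concern.** A model with arm, time and arm-by-time effects, fitted to baseline and six weekly scores, has a free mean for every arm at every time, including baseline. With complete data its baseline-to-week-6 contrast is the unadjusted difference in mean changes. Any chance difference in baseline score that remains after stratification passes one for one into that contrast.

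Because baseline precedes treatment and the trial is double-blind, the true baseline means are equal by design. A model that uses this adjusts for the observed baseline difference by the regression slope rather than by a slope of 1, and is usually more precise.

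The stake is precision on a small comparison of 26 against 26. The first test is a gatekeeper: if the 5.0 mL contrast misses p ≤ .10, the 2.5 mL comparison becomes exploratory.

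**Working it through.** **Inputs.** Section 13.5: 26 evaluable patients per oxybutynin arm and 13 + 13 = 26 on pooled placebo; two-sided α = .10; standardized difference d = 0.50; "intraclass correlation of .50"; stated power 76%. Write ρ for the baseline-to-week-6 correlation and k for the ratio of week-6 SD to baseline SD. The documents give neither. I take ρ = .50 from the planning ICC and k = 1, then vary both.

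**The plan's own figure.** The mean of six weekly scores under compound symmetry has variance (1 + 5 × .50)/6 = 0.583. Then 0.50/√(0.583 × 2/26) = 2.36, and power = Φ(2.36 − 1.645) = 76%. The stated power is thus reproduced by an effect averaged over six weeks. The test in Section 13.4 is at week 6, where 0.50/√(2/26) = 1.80 and power is 56%. That gap is a separate matter, but it explains why 56% is the starting point below.

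**Variance of the week-6 contrast** (baseline SD = 1, complete data):

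- Free baseline means: (1 + k² − 2ρk)(1/26 + 1/26)
- Common baseline mean: k²(1 − ρ²)(1/26 + 1/26)
- The first bracket minus k²(1 − ρ²) is (1 − ρk)², which is never negative.

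At ρ = .50, k = 1 these give 0.0769 and 0.0577, a 25% cut. The standard error falls 13% (√0.75 = 0.866), and the 90% half-width falls from 0.456 to 0.395 SD. Generalized least squares on the full layout (three groups of 26, seven visits) gives the same values. In model-based terms the gain equals 26/0.75, or about 35 patients per group.

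**Power at d = 0.50:** 56.3% to 66.9% (normal), or 55.7% to 66.2% (noncentral t).

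**Sensitivity of the variance cut.** With k = 1 the cut is (1 − ρ)/2. The power column takes d in change-score SD units, so the planned model stays at 56%.

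| ρ | Variance cut | Power after |
|---|---|---|
| .3 | 35% | 72% |
| .5 | 25% | 67% |
| .7 | 15% | 62% |
| .8 | 10% | 60% |

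Change-score units are a reasonable reading of d. Section 1.2 reports "5.0 mg (-16.9, SD 15.6) treatment arms compared to placebo (-5.7, SD 10.2"), and (16.9 − 5.7)/√((15.6² + 10.2²)/2) = 11.2/13.18 = 0.85, the benchmark quoted in Section 13.5.

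At ρ = .50 the cut is 1 − 0.75k²/(1 + k² − k): 48%, 25%, 4% and 0% for k = 0.75, 1.0, 1.5 and 2.0.

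**Cost of estimating the slope:** about 1/(78 − 3 − 2) = 1/73 = 1.4% of variance.

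**Dropout.** With monotone dropout of 10% the variance goes from 0.0835 to 0.0642 (−23%); with 20%, from 0.0891 to 0.0699 (−22%).

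**Stratified allocation.** I used simulation, with 20,000 trials per setting, N = 78 and 2:2:1:1 minimization on three binary factors. One factor was a dichotomized proxy for baseline score. Assumed inputs were a proxy correlation of .80–.95 and a biased-coin probability of 0.85.

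| | Change contrast | Baseline-adjusted |
|---|---|---|
| True variance | 0.067–0.071 | 0.057–0.059 |
| Model-based variance | 0.077 | 0.058 |
| Type I error (nominal 10%) | 7.8–9.0% | 9.6–10.3% |
| Power | 56% | 65–66% |

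Stratification thus recovers part of the precision by design, but the planned model does not credit it. The true variance cut is about 14–18%.

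**Optional covariates.** Adding three binary strata as main effects, under compound symmetry, leaves the contrast variance at 0.0769. A term constant over time cancels from a change.

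**The case against.** The planned model is valid and estimates the contrast it names without bias. Section 13.5 calls the trial a pilot sized on feasibility, so extra efficiency may look optional. That is a fair point about weight, but the change costs almost nothing.

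The size is uncertain. The ICC is stated for a design with six weekly scores, not for the baseline-to-week-6 pair, and no SD ratio is given. The simulation inputs are assumed as well. This stands: the direction is secure, the amount is not. The 25% is also model-based, and 14–18% is the better guide to true sampling variance under this allocation.

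The covariate argument is shown only for main effects under compound symmetry. Stratum-by-time terms would recover part of the gain, and the plan does not rule them out. They are, however, optional and triggered by observed imbalance, so they do not replace a prespecified adjustment.

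The remark that the change contrast is conservative assumes equal variances across arms. Section 1.2 reports change SDs of 7.7, 15.6 and 10.2 in women. If those held here, a pooled variance would be (59.3 + 243.4 + 104.0)/3 = 135.6, against a true average of (243.4 + 104.0)/2 = 173.7 for the 5.0 mL contrast. Before any effect of stratification, its nominal 90% interval would then cover about 85%, and the 2.5 mL interval about 97%. This qualifies the conservatism remark; it does not remove the relative gain from using baseline.

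**Conclusion.** The point holds as a missed efficiency, not an error. The primary model leaves baseline means free by arm although the design makes them equal in expectation, and no other provision in the plan reliably supplies the adjustment.

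Under the planning correlation and equal SDs, the week-6 test gains about 10 percentage points of power. With one covariance matrix shared by all arms, the model-based variance cannot rise apart from the small slope cost, but the gain shrinks toward zero as ρk approaches 1. The common-mean constraint also relies on the blind holding through the drug-free diary week, since that week follows randomization. The change should be made.

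**What to change.** In Section 13.4, for weekly hot flash scores, prespecify one of two models:

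- a constrained longitudinal model, with baseline and weekly scores as outcomes, effects for time and for arm at each post-baseline week, and no arm effect at baseline; or
- a model for the six weekly scores with baseline score and baseline-by-week terms as fixed covariates.

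Keep the same week-6 contrasts, fixed sequence and α. The cost is one sentence and about 1.4% of variance for the slope. No new data or patients are needed, but the choice must be fixed before unblinded data are seen. The figures here do not carry over to the frequency model, which may not be Gaussian, or to the symptom and HFRDIS models, whose contrasts are week-6 differences rather than changes.

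### AIC may replace a converging unstructured covariance in the primary model, so the error rate of the nominal .10 test depends on a structure not fixed in advance: up to about 11% to 13% under some assumed patterns, nominal or conservative under others

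*Combined protocol and SAP*

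**What the plan says.** All of this is in the efficacy and missing-data paragraphs of Section 13.4.

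- **Model.** "a mixed model will be estimated that includes baseline and weekly hot flash scores across the 6-week treatment period", with nominal time, arm and their interaction, and a "residual covariance matrix based on the observed covariances". I read that as unstructured.
- **Selection.** "Alternative structures will be investigated for the residual covariance matrix". The plan then states how one of them is chosen: "with final selection based on convergence of the mixed model and minimization of the Akaike information criterion". No candidates are listed, and no fallback order, degrees-of-freedom method or robust variance is named.
- **Test.** The target is "mean differences in hot flash score reduction from baseline to 6 weeks post-randomization between the oxybutynin and placebo arms". "The contrast will involve a two-sided t-test with a nominal significance level of" .10, with the 5.0 mL arm tested first. The 2.5 mL arm is formally tested only if the first test succeeds: "Finally, if p > .10 for the first test, we will conclude that neither dosing schedule significantly improved hot flash scores".
- **Missing data.** "The primary analysis will provide unbiased parameter estimates under a missing completely at random or missing at random mechanism", with a sensitivity analysis over missing-data assumptions.

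Section 13.5 gives 26 evaluable patients per oxybutynin arm, 13 per placebo arm (pooled to 26), and an intraclass correlation of .50. It gives no correlation or SD by week. Sections 7.0 and 7.1 make Days 1 to 7 an untreated baseline week.

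**The concern.** AIC rewards average fit over the whole covariance matrix and charges for each parameter. The primary test depends on three elements of that matrix: the baseline variance, the week 6 variance and their covariance. A structure with few parameters can fit most of the matrix well, win on AIC, and still be wrong for that one pair.

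Baseline is the week most likely to be the odd one out, because every man, placebo included, starts a blinded treatment on Day 8. If its correlation with later weeks is lower than theirs with each other, compound symmetry overstates the baseline-to-week-6 correlation and makes the standard error too small. The 90% interval is then too narrow and the gate to the 2.5 mL comparison opens too often. Section 13.4 states that Type I error is to be controlled and draws formal conclusions from p against .10, so the pilot label in Section 13.5 does not make this irrelevant.

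**Working it through.** **Inputs from the documents.** Seven time points; 78 men in three analysis arms of 26, so 78 − 3 = 75 degrees of freedom with complete data; two-sided .10 (critical t = 1.665); ICC .50. **Assumed:** the other correlation patterns, the SD ratios and the candidate lists.

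**1. The plan's own figure.** Section 13.5 states 76% power. Under compound symmetry with ICC .50, the SD of a six-score mean is √((1 + 5 × .50)/6) = .764. The standard error is .764 × √(2/26) = .212, and .50/.212 = 2.36. Power is Φ(2.36 − 1.645) = 76%. The figure reproduces, so compound symmetry is the planning model. (It is power for a six-week average. The contrast actually tested gives .50/√(2/26) = 1.80 and about 56%, which is a separate matter.)

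**2. Where the structure enters.** With complete data the estimate is the difference in mean change, whatever the structure. Its squared standard error is V × 2/26, with V = Var(baseline) + Var(week 6) − 2 Cov(baseline, week 6). A true error of 13% needs V understated by about 15%.

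**3. What AIC charges.** Unstructured has 7 × 8/2 = 28 parameters and compound symmetry has 2. Unstructured is kept over it only if −2 log-likelihood improves by more than 2 × 26 = 52. One of the 7 × 6/2 = 21 week pairs enters the test.

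**4. Size by hand, then by simulation.** Take equal SDs, correlation b between baseline and each treated week (6 pairs), and p among treated weeks (15 pairs). Compound symmetry fits roughly r = (6b + 15p)/21. The fitted-to-true ratio of V is (1 − r)/(1 − b), and the error if compound symmetry were always used is P(|t₇₅| > 1.665 × √ratio). For .40/.60: r = (2.4 + 9.0)/21 = .543, ratio = .457/.600 = .762, error 15.0%.

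The last two columns simulate the null with complete normal data, REML, and AIC choosing among unstructured, compound symmetry and AR(1).

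| b / p | r | V ratio | Error, compound symmetry always | Compound symmetry chosen | Error with AIC |
|---|---|---|---|---|---|
| .50/.60 | .571 | .857 | 12.7% | 97% | 12.3% |
| .50/.65 | .607 | .786 | 14.4% | 87% | about 13% to 14% |
| .40/.60 | .543 | .762 | 15.0% | 78% | about 13.4% |
| .50/.70 | .643 | .714 | 16.3% | 56% | about 13% |

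Unstructured fixed in advance gave 9.6% to 10.6% across all runs, which is nominal within simulation error.

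**5. Where the inflation shrinks, vanishes or reverses.**

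- *Plan's own pattern* (.50 throughout): 9.5% to 9.9%.
- *Large misfit:* AIC returns to unstructured. .50/.75 gives 10.8% and .50/.80 gives 10.1%.
- *Unequal SDs* (baseline-to-treated ratio 1.25, 1.54, 0.8; candidates unstructured, compound symmetry, heterogeneous compound symmetry, AR(1), Toeplitz): .50/.65 gives 11.3%, 11.2%, 11.3%; .40/.60 gives 11.9%, 10.7%, 11.1%.
- *Richer lists, equal SDs:* adding Toeplitz and the usual heterogeneous forms leaves baseline-distinct patterns at 12.7% to 13.0%. In another run, also including a one-factor structure and heterogeneous AR(1) brought .50/.65 to 11.4%.
- *Random intercept and modest slope:* 13.8% with the three-structure list, about 11% once Toeplitz is offered.
- *Slowly decaying correlation:* with the three-structure list AIC mostly picks AR(1) and the error falls to about 6%. With Toeplitz added it is 9.6%.

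**6. Price of fixing unstructured.** With compound symmetry true at .50 and a standardized difference of .50, one run gave 55.2% power for both structures; another put the loss at 0.4 points.

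**The case against.** The strongest reply is that the plan starts from the observed covariances, states an objective selection rule in advance, and is a feasibility-sized pilot. AIC selection of a covariance is accepted practice. The 13% needs three things the documents do not supply: a baseline-distinct correlation pattern, nearly equal SDs at every week, and a particular candidate list. Section 1.2 reports hot flash frequency in women falling 60% and 77% on drug against 27% on placebo, so a spread that changes after baseline is plausible, and the inflation then drops to a point or two. Under the one correlation figure in the documents there is none.

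Most of that stands, and it limits the size of the point. It does not remove it. The error rate depends on which unlisted structures are tried and on a correlation pattern unknown beforehand. The alternative holds 10% in every pattern run and gives up almost nothing.

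A reader might also infer that selection with the arm contrasts in view invites choosing the structure that gives the better p-value. The text does not support that. Convergence and minimum AIC do not use the treatment p-value, and nothing says the contrasts will be inspected first.

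**Conclusion.** The point holds as a cheap improvement to the primary analysis. AIC can discard a converging unstructured matrix in favour of one that misfits the only pair of weeks tested. Where the baseline week is less correlated with treated weeks than they are with each other, the true error of the nominal .10 test can reach about 11% to 13%. The upper end needs near-equal SDs across weeks (single runs with the three-structure list reached 14.0%); with a different baseline SD it is about 10.5% to 12%. It is nominal at the plan's ICC of .50 and can fall to about 6%.

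Two stronger readings are not supported. One is that the primary test runs at 13%: the documents establish neither that size nor even a liberal direction. The other is that the statement of unbiasedness under missing at random fails. With incomplete data that property does lean on an adequate covariance model, but every calculation here used complete normal data with equal covariance across arms, so no bias has been shown.

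**What to change.** In Section 13.4:

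1. Name the unstructured residual covariance, with Kenward-Roger degrees of freedom, as the primary structure.
2. Remove AIC as a criterion for the primary model.
3. List fallback structures in a fixed order, to be used only if the unstructured model fails to converge, with sandwich standard errors.
4. Report AIC-selected structures as sensitivity analyses.

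The cost is wording: no patients and no data collection. The downside is a power loss under about half a point if compound symmetry is true.
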